## 9.1 PRIMARY EFFICACY VARIABLE

The primary endpoint analysis is an evaluation of the difference between the two treatment groups in mean fluid balance (L) at 72 hours or ICU discharge, whichever occurs first. The following hypothesis will be tested:

$$\begin{aligned}H_0: \mu_c - \mu_t &= 0 \\H_a: \mu_c - \mu_t &\neq 0\end{aligned}$$

where  $\mu_t$  and  $\mu_c$  is the average fluid balance in the Starling SV and control groups, respectively. Statistical summaries will include means, medians, quartiles and standard deviation for each

treatment group, as well as 95% confidence interval of the difference between treatment group means. Subjects that enter the study on dialysis, or are on chronic dialysis, are excluded from this endpoint. A two-sample t-test will be used to test the null hypothesis at a two-sided 0.05 level of significance. A significant p-value combined with a lower sample mean for Starling SV than for the control group will indicate statistical superiority of Starling SV over the control with respect to the primary endpoint. Fluid balance will be analyzed under sensitivity analyses not intended for formal hypotheses testing.

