8.6 Subject Randomization

Subjects will be randomized to either the treatment or control arm of the study once the decision has been made to admit the patient to the ICU. Any patients that are enrolled but are not admitted to the ICU, or who receive > 3L of treatment fluid prior to randomization will be considered a screen failure and will be exited from the study at this time.

Subjects will be randomized in a 2:1 treatment to control ratio to increase power for sub-analysis by patient population. Additionally, subject randomization will be stratified to ensure even randomization between the three time windows of enrollment (0-6 hours, 6-12 hours, 12-24 hours)

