STUDY DESIGN	This study is a prospective, multi-center, randomized trial comparing the mean difference in fluid balance and associated patient outcomes between a treatment guided by a dynamic assessment of fluid responsiveness and a standard of care control group not using dynamic fluid assessment.

	
Subjects will be randomized in a 2:1 treatment to control group ratio to increase power for sub-analysis by patient population. Subject randomization will be stratified by time window of enrollment to ensure even randomization between the three time windows of enrollment (0-6 hours, 6-12 hours, and 12-24 hours).
 
Patients randomized to the Starling SV arm will have treatment guided by a dynamic assessment of fluid responsiveness (measured by a change in stroke volume index > 10%) as assessed by passive leg raise (PLR).
 
Patients randomized to the control group will receive standard of care treatment. The use of dynamic fluid assessment (i.e. SVV, PPV, or SV change) to determine fluid responsiveness within the control group is prohibited.

INTERIM ANALYSES	
An interim analysis is planned after 90 subjects have been enrolled and completed the evaluation of the key secondary endpoint of change in serum creatinine at 72 hours. At this analysis, a sample size re-estimation will occur in order to determine promise for superiority in the key secondary endpoint.
 
No annual reports for the FDA are anticipated prior to the end of data collection as this study is not intended to support a regulatory filing.
 
An annual report and project status update may be requested by the local IRB at study sites.
 
No other interim analyses are planned.

FINAL ANALYSES	
All final planned analyses identified in this SAP will be completed after the last subject has completed their 30 day follow up.

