## 5 SAMPLE SIZE

Subjects will be randomly assigned in a 2:1 ratio to treatment with Starling SV or to treatment with standard of care, stratified by time window of enrollment (0-6 hours, 6-12 hours, and 12-24 hours). The primary effectiveness endpoint for this study is fluid balance at ICU discharge.

Minimum enrollment ( $N_{\min}$ ) in the study will be set at 120 subjects (80 Starling SV and 40 control) to power at 80% for demonstration of superiority of means for the secondary endpoint of creatinine levels as a measurement of change from baseline at 72 hours. The secondary endpoint for change in creatinine levels at 120 evaluable subjects displays 80% power at a two-sided alpha level of 0.05 to demonstrate superiority of Starling SV under an assumption of an average treatment effect of -1.4 mg/dL with a standard deviation of 2.5 mg/dL.

Under an assumption of an average treatment effect of -2 L with a standard deviation of 3 L, the sample size of 120 evaluable subjects provides 92.7% power in a test of superiority of means for the primary effectiveness endpoint at a two-sided 0.05 level of significance.

The trial will incorporate a sample size re-estimation (SSR) at the time of the interim look (after 90 patients have been evaluated for the key secondary endpoint) based on promise for superiority in the key secondary endpoint. Sample size re-estimation, described in further detail in Section 3.1, will result in a maximum of 210 total evaluable subjects, or no more than 1.75 times the minimum of 120.

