### 6.4 PER-PROTOCOL (PP)

Subjects will be included in the Per-protocol group if they sign the ICF, are randomized and have the assigned procedure completed, meet critical study eligibility criteria and have no major protocol deviations (to be pre-defined as an attachment to the interim and final analyses), and, in the treatment group, receive monitoring for the first 72 hours of study enrollment. The PP population represents the primary analysis population for the primary and secondary endpoints.

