### 7.6 ASSESSMENT OF HOMOGENEITY

To evaluate difference among sites in the study, summaries of baseline variables and endpoints by site will be tabulated for the PP analysis set. Comparisons will be made across sites for selected baseline variables. Continuous baseline data will be compared across sites for the PP analysis set using one-way ANOVA; categorical data will be compared across sites using the chi-square test.

To assess consistency in the treatment effect on the primary endpoint and on continuous secondary endpoints across sites, two-way ANOVAs with the main effects of treatment group and site and with the treatment group by site interaction effect will be carried out on the PP and mITT analysis sets. An endpoint with an interaction effect that is not significant at the 0.15 level of significance will be considered as supporting the poolability of data across sites for the treatment comparisons on that endpoint. Otherwise, treatment comparisons within sites will be inspected to determine the direction and magnitude of the interaction; if treatment effect is consistent in direction across sites centers but only differs in magnitude across sites, poolability of sites for the endpoint analysis is also supported. Any site with fewer than six subjects (combined treatment and control) will be combined into a single pooled site for purposes of this analysis.

The above assessment of consistency will be repeated across the following subgroups, with appropriate descriptive statistics being presented for each treatment group within each subgroup category:

- Patient disease state
- Patients determined to be fluid responsive vs non-fluid responsive
- AKI measures in patients determined to increase serum creatinine levels from baseline vs decrease serum creatinine levels from baseline (AKI measures vs. no AKI measures)
- Enrollment time frame (0-6 hours, 6-12 hours, 12-24 hours)
- Sex

Dichotomous secondary endpoint data will similarly be analyzed for poolability using logistic regression analysis.

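### Randomisation is stratified by enrollment window, but the formal primary t-test and its 95% CI leave the window out; if the window predicts fluid balance, some precision is lost

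*SAP*

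**What the plan says.** Three places set out the stratification. Protocol 8.6 states that "subject randomization will be stratified to ensure even randomization between the three time windows of enrollment". The SAP Summary repeats it ("Subject randomization will be stratified by time window of enrollment to ensure even randomization"), and SAP 5 lists the levels: "stratified by time window of enrollment (0-6 hours, 6-12 hours, and 12-24 hours".

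The formal primary analysis does not use the factor. SAP 9.1 says: "A two-sample t-test will be used to test the null hypothesis at a two-sided 0.05 level of significance". The interval it reports is the 95% CI for the difference between the two group means, with no adjustment mentioned. Protocol 12.3 and the Statistical Design row of the Protocol Synopsis also specify t-tests without the window.

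The window is modelled in one place only, the consistency assessment in SAP 7.6, where it is listed as a subgroup: "Enrollment time frame (0-6 hours, 6-12 hours, 12-24 hours". That assessment fits treatment, window and their interaction in the PP and mITT sets. It supplies neither the primary p-value nor the primary CI. SAP 9.1 also promises further analyses without naming them: "Fluid balance will be analyzed under sensitivity analyses not intended for formal hypotheses testing".

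Two provisions affect who is analysed. SAP 6.4 says "The PP population represents the primary analysis population for the primary and secondary endpoints", and SAP 9.1 says "Subjects that enter the study on dialysis, or are on chronic dialysis, are excluded from this endpoint".

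**The concern.** Stratified randomisation removes chance differences between arms in the stratifying factor. If that factor predicts the outcome, the treatment difference varies less from trial to trial than a two-sample t-test assumes, because the t-test keeps the between-window variation in its error term. The standard error is then too large, the interval wider than it need be, and the test runs below its nominal level.

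The primary test carries extra weight here. Under SAP 7.5 and 9.2.1 the six formal secondary endpoints are tested only if it succeeds. Under SAP 3.1.1 it must succeed at 120 subjects and again at the final size if the sample is increased. Its CI is also the trial's main estimate of effect. Precision given up here is given up for no saving, because the window is already known for every randomised subject.

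**Working it through.** **Inputs from the documents** (SAP 5): 120 subjects split 80:40, effect 2 L, SD 3 L, two-sided 0.05, stated power 92.7%.

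**Assumptions.** The documents give no R² (share of within-arm variance explained by the window), block size or list structure. I take R² from 0 to 20%, and treat 3 L as the total within-arm SD, including variation between windows. The 80:40 split is kept for illustration, although the PP rule and the dialysis exclusion will make the analysed set smaller.

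**Step 1. The plan's own figure.**
- SE = 3 × √(1/80 + 1/40) = 3 × √0.0375 = 0.581 L.
- Noncentrality = 2 / 0.581 = 3.443, on 118 df.
- Noncentral t power = 92.71%, which matches 92.7%.
- CI half-width = 1.980 × 0.581 = 1.150 L.

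**Step 2. Window in the model, exact balance.** Residual SD = 3 × √(1 − R²), on 116 df (two more parameters).

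| R² | Residual SD (L) | Half-width (L) | Power at 2 L |
|---|---|---|---|
| 0 | 3.000 | 1.151 | 92.7% |
| 2% | 2.970 | 1.139 | 93.2% |
| 10% | 2.846 | 1.092 | 94.9% |
| 20% | 2.683 | 1.029 | 96.8% |

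The unadjusted half-width stays near 1.150 L. It is therefore about 5% too wide at R² 10% (1.150 / 1.092 = 1.053) and about 12% too wide at 20% (1.150 / 1.029 = 1.118).

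**Step 3. True size of the t-test under exact balance.** Size ≈ 2 × [1 − Φ(1.96 / √(1 − R²))].
- R² 10%: 1.96 / 0.949 = 2.066, giving 3.9%.
- R² 20%: 1.96 / 0.894 = 2.191, giving 2.8%.

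**Step 4. Simulation with realistic balance.** N = 120, 2:1, blocks of 6. Three equally likely windows have effects −a, 0, +a, with a = √(13.5 × R²) L, so that the window variance 2a²/3 equals R² × 9. There were 20,000 trials per cell, or 12,000 for 8 and 18 sites; Monte Carlo SE is about 0.15 to 0.2 points for size. The range of 8 to 18 sites is the Synopsis figure: 7 US + 1 UK up to 15 US + 3 UK.

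| List structure | t-test size, R² 10% / 20% | Power at 2 L, t-test / window model, R² 10% | Same, R² 20% |
|---|---|---|---|
| Central, by window | 3.9% / 2.8% | 93.6 / 94.8% | 94.5 / 96.7% |
| Site × window, 8 sites | 4.2% / 3.4% | 93.3 / 94.8% | 94.2 / 96.9% |
| Site × window, 12 sites | 4.2% / 3.6% | 93.3 / 94.7% | 93.9 / 96.6% |
| Site × window, 18 sites | 4.5% / 4.1% | 93.3 / 94.7% | 93.6 / 96.6% |
| No balance within windows | 4.9% / 4.8% | not run | not run |

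The window model held 5.0% in the central and 12-site runs. At R² 0 its power was 0.1 to 0.2 points below the t-test; at R² 2% it was 0.1 to 0.2 points above.

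**Step 5. A smaller true effect.** If the effect were 1.5 L rather than 2 L (an assumption), power with central blocks for t-test / window model was 73.8 / 77.1% at R² 10% and 74.3 / 81.2% at R² 20%.

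**The case against.** The strongest reply is that nothing in the plan is wrong. The t-test is valid, slightly conservative at worst, consistent with the protocol and with its own sample-size calculation. The documents give no reason to think the window predicts fluid balance; the stated purpose of stratifying is only even allocation. At R² of 0 to 2% the power change is −0.2 to +0.2 points, no larger than simulation noise. Even at 10 to 20% it is a few points on a base above 92%. The gain also depends on how closely the arms balance within windows. In a fixed layout of 27:13, 27:13 and 26:14, for example, simulated power at 2 L was 94.5% against 94.7% at R² 10% and 95.9% against 96.8% at R² 20%. SAP 7.6 will show whether the window matters. Finally, the change replaces a protocol-specified test.

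Most of this stands, and it is why the point is optional. Two parts do not carry. First, the fixed layout happens to place one treated subject fewer in the highest window, which shifts the unadjusted difference in treatment's favour by 3a/80, about 0.04 to 0.06 L. It therefore understates the usual gain; under exact balance the gain is about 1.1 and 1.9 points. Second, the SAP 7.6 model tests consistency and cannot replace the formal p-value or CI once results are known. The SAP also already adjusts one endpoint by ANCOVA (creatinine, 9.2.1.1), so a covariate model is not foreign to it.

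**Conclusion.** The concern holds as a precision point of low severity. It is not a validity error: type I error is not inflated and the 92.7% is right. The formal primary test and CI omit the factor used to randomise, and no other analysis in the SAP supplies an adjusted formal result.

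The size is conditional. If the window explained 10% or 20% of the variance, the half-width would fall from 1.15 L to about 1.09-1.10 or 1.03 L, and power at 2 L would rise by roughly 1 to 1.5 or 2 to 3 points. The gain would be larger if the true effect were nearer 1.5 L. If the window explained nothing, there would be no gain and a negligible loss. The conservatism of the t-test fades as balance within windows weakens, whether through many site-level lists or through exclusions from the PP set. Confidence is medium, because R², block size, list structure and the reading of 3 L as total SD are all assumed.

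**What to change.** In SAP 9.1, define the primary analysis as a linear model of fluid balance on treatment and the three-level enrollment window as randomised. Test the treatment coefficient at two-sided 0.05, and report the adjusted difference with its 95% CI. Use the same model at 120 subjects and, if the sample is increased, at the final size. Name the unadjusted t-test as a sensitivity analysis. Make the change before any comparison of the arms on fluid balance, so before the analysis at 120. Either align Protocol 12.3 and the Synopsis Statistical Design text, or record the departure in the SAP.

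The cost is two degrees of freedom, one model statement and the wording. No new data are needed. If the window predicts nothing, the interval is about 0.1 to 0.4% wider (simulated half-width 1.149 to 1.150 L with central lists, 1.152 to 1.156 L with site lists).

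Two further steps are optional and separate. Pre-randomisation fluid volume could be added as a covariate, but only if that total is actually recorded. The window could also enter the creatinine ANCOVA in SAP 9.2.1.1, in which case the interim conditional-power statistic in SAP 3.1.1 must be brought into line.

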8.3 Exclusion Criteria

Subjects must not have any of the following exclusion criteria:

1. Primary diagnosis of: acute cerebral vascular event, acute coronary syndrome, acute pulmonary edema, status asthmaticus, major cardiac arrhythmia, drug overdose, or injury from burn or trauma
2. Known aortic insufficiency, or aortic abnormalities
3. Hemodynamic instability due to active hemorrhage, (e.g. gastrointestinal bleeding/coagulopathy/trauma)
4. Patient has received > 3 liters of IV fluid prior to study randomization
5. Requires immediate surgery
6. Patient transferred to the ICU from another hospital unit
7. Do not attempt resuscitation (DNAR or DNR) order
8. Advanced directives restricting implementation of the resuscitation protocol
9. Contraindication to blood transfusion
10. Attending clinician deems aggressive resuscitation unsuitable
11. Transferred from another in-hospital setting
12. Not able to commence treatment protocol within 1 hour after randomization
13. Known intraventricular heart defect, such as VSD or ASD
14. Use of additional hemodynamic monitoring involving SVV, PPV or SV changes to determine fluid responsiveness
15. Seizure in the last 24 hours
16. Prisoner
17. Pregnancy

18. Age <18
19. Known allergy to sensor material or gel
20. Inability or contraindication to doing a passive leg raise with both extremities, such as inability to interrupt venous compression boots
21. Patient has an epidural catheter in place
22. Suspected intra-abdominal hypertension
23. Inability to obtain IV access
24. Diabetic ketoacidosis
25. Hyper-osmolarity syndrome
26. Patient treatment uncouples from the treatment algorithm

27. Patient should be excluded based on the opinion of the Clinician/Investigator

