9.4 Schedule of Assessments

Each subject will follow a schedule of assessments and events from which data will be collected (Table 1).

Table 1: Schedule of Assessments

Assessment/Event	Pre-Consent	Consent	Baseline	Enrollment-72 hours	72 hours-Discharge
Subject Identification	X				
Determine Eligibility	X				
Informed Consent		X			
Medical History			X	X	X
Physical Exam, limited, and lab values			X		
Urine Sample			X		
Optional plasma serum collection (two, 5ml samples to be frozen for possible future testing)			X		
Serum Creatinine			X	X	X (chart review)
Medications, specific			X	X	X
Volume resuscitation fluid			X	X	
Respiratory Status			X	X	X

Assessment/Event	Pre-Consent	Consent	Baseline	Enrollment-72 hours	72 hours-Discharge
(intubated, ventilated)					
Starling SV System			Attached	Continuous hemodynamic recordings	
Fluid Assessment				X	
Adverse events				X (+48 hours)	

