12.3 Primary Endpoint Analysis

The primary endpoint is an evaluation of the difference between the two treatment groups in mean fluid balance (L) at 72 hours or ICU discharge, whichever occurs first. The following hypothesis will be tested:

$$H_0: \mu_C - \mu_T = 0$$

$$H_a: \mu_C - \mu_T \neq 0$$

where μ_T and μ_C is the average fluid balance in the Starling SV and control groups, respectively. Statistical summaries will include means, medians, and standard deviation, as well as 95% confidence intervals. A t-test for superiority at a significance level of 0.025 will be performed to test the hypothesis that μ_T is significantly less than μ_C . If it can be established that the difference is greater than 0 points (i.e. $\mu_C > \mu_T$), superiority will also be claimed.

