## 8 DEMOGRAPHICS AND OTHER BASELINE CHARACTERISTICS

### 8.1 DEMOGRAPHICS

Demographics will be summarized by treatment group for the PP and mITT analysis sets. There will be no formal statistical comparisons between treatment groups on demographic variables. The continuous variables of age, height (cm), weight (kg), BMI, qSOFA, SOFA, FiO2, and Glasgow Coma Score will be summarized by treatment group using sample size, mean, standard deviation, minimum and maximum. For the categorical variables of sex (male, female), race (white, black or African American, American Indian/Alaska Native, Asian, Native Hawaiian or Other Pacific Islander, other, unknown), ethnicity (Hispanic or Latino, Not Hispanic or Latino, Unknown), known or presumed infection, SIRS criteria exhibited (Temperature >38 C, Temperature <36 C, Heart Rate > 90/min, Respiratory rate >20/min or PaCO2 <32mm, White Blood Cell Count >12000/mm^3, White Blood Cell Count <4000/mm^3, White Blood Cell Count

[REDACTED]

>10% Immature Cells), smoking history (never, current, former), sepsis diagnosis (bacterial, fungal, viral, parasitic, other), Receiving Respiratory Support, and Cardiovascular Score (MAP  $\geq$  70 mmHg, MAP < 70 mmHg, Dopamine <5 or dobutamine (any dose), Dopamine 5.1-15 or epinephrine  $\leq$ 0.1 or norepinephrine  $\leq$ 0.1, Dopamine >15 or epinephrine >0.1 or norepinephrine >0.1), the number and percentage of patients in each category will be presented for each treatment group.

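### The primary fluid-balance t-test is valid but unadjusted, so precision available from baseline data goes unused

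*SAP*

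**What the plan says.** SAP 9.1 specifies the primary test: "A two-sample t-test will be used to test the null hypothesis at a two-sided 0.05 level of significance". Protocol 12.3 has the matching test, worded for one direction: "A t-test for superiority at a significance level of 0.025 will be performed". The protocol synopsis (Statistical Design) also prescribes t-tests for continuous endpoints. None of these places names a covariate or the stratification factor.

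Nothing else in the plan adjusts the primary comparison:

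- The sensitivity analyses mentioned in SAP 9.1 are not described.
- The two-way ANOVAs in SAP 7.6 assess consistency across sites and subgroups.
- The demographic variables in SAP 7.3 enter only the imputation model.

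The candidate covariates appear as follows:

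- **SOFA and weight.** SOFA is a baseline assessment in protocol 9.1. SAP 8.1 summarises both by arm: "The continuous variables of age, height (cm), weight (kg), BMI, qSOFA, SOFA, FiO 2 , and Glasgow Coma Score".
- **Fluid before randomisation.** Protocol 8.3 excludes a subject if "Patient has received > 3 liters of IV fluid prior to study randomization", and protocol 8.2 requires refractory hypotension after 1 L. The schedule in protocol 9.4 has a row "Volume resuscitation fluid" marked at Baseline. SAP section 8 does not list this volume among the baseline variables.
- **Enrollment window.** Randomisation is stratified by three windows (protocol 8.6, SAP section 5).

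**The concern.** Sicker or heavier patients, and those who have already had more fluid, may plausibly differ in how much fluid they accumulate over the next 72 hours. If so, part of the outcome variance is predictable at randomisation. An unadjusted t-test leaves that part in the error term, so the confidence interval is wider than it needs to be.

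Two features raise the stakes. The control arm has only 40 subjects at the planned size. The primary result also gates every formal secondary claim (SAP 7.5 and 9.2.1), and if the sample size is increased it must be met both at 120 and at the final size (SAP 3.1.1). Adjustment has to be prespecified to be credible, because covariates chosen after seeing the results invite doubt.

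**Working it through.** **Inputs from the documents.** SAP section 5 gives the effect and spread: "Under an assumption of an average treatment effect of -2 L with a standard deviation of 3 L". It gives the size as "120 subjects (80 Starling SV and 40 control"), and the stated power: "the sample size of 120 evaluable subjects provides 92.7% power in a test of superiority of means". Alpha is two-sided 0.05.

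**Step 1: reproduce the plan's figure.** SE = 3 × √(1/80 + 1/40) = 0.581 L. The noncentrality is 2/0.581 = 3.44 on 118 degrees of freedom. Noncentral-t power is 92.7%, which matches. The stated power is therefore that of the unadjusted, two-sided 0.05, 2:1 t-test.

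**Step 2: add covariates.** The documents give no R-squared between the covariates and fluid balance, so it is an assumption, shown as a range. The residual SD is 3 × √(1 − R²), three degrees of freedom are removed (df = 115 for SOFA, weight and prior fluid), and the equivalent unadjusted size is 120/(1 − R²).

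| Assumed R² | SE (L) | 95% CI half-width (L) | Power at 2 L | Power at 1.5 L | Equivalent unadjusted N |
|---|---|---|---|---|---|
| 0 | 0.581 | 1.15 | 92.7% | 72.6% | 120 |
| 5% | 0.566 | 1.12 | 93.9% | 74.8% | 126 |
| 10% | 0.551 | 1.09 | 94.9% | 77.0% | 133 |
| 20% | 0.520 | 1.03 | 96.8% | 81.7% | 150 |
| 30% | 0.486 | 0.96 | 98.3% | 86.4% | 171 |

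The 1.5 L effect is an assumption and is not in the documents. The same column applies to a 2 L effect if the SD is really 4 L, because 2/4 = 1.5/3.

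**Step 3: cost when the covariates are useless.** Losing three degrees of freedom alone leaves power at 92.7%. Chance imbalance in the covariates also inflates the variance, on average by about (N − 3)/(N − 3 − k). With k = 3 this is 117/114 = 1.026, so the SE becomes 0.581 × √1.026 = 0.589 L and power at R² = 0 is 92.1%. The same allowance gives 94.4%, 96.5% and 98.1% at R² = 10%, 20% and 30%. Break-even is near R² = 1 − 114/117 = 2.6%. With two further terms for enrollment window it is at most about 1 − 112/117 = 4.3%.

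**Step 4: cost of missing covariates.** If 10% of subjects lacked a covariate and were dropped (an assumption; 72 and 36 left), power at 2 L would be 92.7% at R² = 10%, no better than the plain t-test, and 89.9% at R² = 0. The benefit therefore depends on keeping those subjects in the model.

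**The case against.** The strongest reply is that nothing is broken. A two-sample t-test in a randomised trial is valid, its standard error already allows for chance baseline imbalance, and it is the test on which the 92.7% rests. The size of 120 was set by the creatinine endpoint, so the primary already has comfortable power, and the gain at 2 L is about 1 to 6 points for R-squared of 5% to 30%. No document shows that the covariates predict fluid balance, and eligibility restricts prior fluid to roughly 1 to 3 L. All of this stands, and it limits the point to efficiency.

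A reader might go further and infer that imbalance in prior fluid is likely and passes directly into the primary difference. The documents do not support that. They do not say when the fluid-balance clock starts, so fluid given before enrollment may not be counted at all, and randomisation makes imbalance possible rather than expected. A reader might also see an inconsistency with the creatinine endpoint, which SAP 9.2.1.1 adjusts. That model adjusts a change score for its own baseline, and fluid balance has no stated baseline value, so the comparison shows only that the plan accepts covariate adjustment.

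Three practical objections also stand and shape the fix:

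- The case report form is not shown, so a cumulative pre-randomisation volume may not exist as a field.
- Blood gas is collected only when available (protocol 9.1), so SOFA components may be missing.
- With 2:1 allocation, a common-slope model is not guaranteed to gain if slopes differ between arms.

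None of these is a reason against a prespecified adjusted analysis.

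**Conclusion.** The point holds as unused precision, not as a flaw in validity. Under the plan's own assumptions, adjustment moves power from 92.7% to between 93.9% and 98.3% for R-squared of 5% to 30%. It narrows the CI half-width from 1.15 L to between 1.12 and 0.96 L. If R-squared is near zero there is no gain and a loss of under one point with three covariates (Step 3). The benefit is more material if the true effect is 1.5 L, where 72.6% becomes 74.8% at R-squared 5% and 81.7% at 20%.

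These results rest on an assumed R-squared, on 120 evaluable subjects, and on the SD of 3 L. The last two are open to question. The SAP analyses efficacy primarily in per-protocol subjects (section 6.4 and section 9) and excludes subjects on dialysis from this endpoint (9.1). The sample-size sections also describe the endpoint as fluid balance at ICU discharge rather than at 72 hours or ICU discharge. The figures measure the gain over an unadjusted test; the gain over a model that already contains the enrollment window is unknown and may be smaller.

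**What to change.** Before any unblinded look:

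1. Make the formal primary analysis a linear model of fluid balance on treatment, enrollment window, baseline SOFA, weight and pre-randomisation fluid volume. Include the last only after confirming that the case report form holds it as a cumulative volume up to randomisation.
2. Impute missing covariates simply, from baseline data alone and without reference to arm or outcome, so that no subject is dropped.
3. Centre the covariates and use treatment-by-covariate terms or robust standard errors, because allocation is 2:1.
4. Report the adjusted difference with its 95% CI, and keep the two-sample t-test as supportive.
5. Align the protocol synopsis (Statistical Design) and protocol 12.3, which both specify a t-test.

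The cost is a few degrees of freedom, a small variance penalty if the covariates turn out not to predict the outcome, and a wording change in both documents. No extra patients are needed and, provided the prior-fluid field exists, no new data.
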